3.1.3. Imaging procedures

One brain MRI will be performed on each subject using a 3 T Philips scanner. Sequences performed will include 3D T1 (MPRAGE, 180 slice 1 mm resolution, 256 x 256 voxel count) for volumetric analysis and clinical sequences to exclude subjects with significant intracranial pathology unrelated to AD, such as malignant brain tumor or subdural hematoma. PET scans will take place on a Biograph mCT PET scanner (Siemens Healthcare) at the CUMC Kreitchman PET Center. Subjects will have one PET scan with ¹⁸F-THK-5351 (injected activity up to 5 mCi = 185 MBq). PET imaging will be performed without arterial sampling. Vital signs (blood pressure, heart rate, respiratory rate, and temperature) will be checked prior to injection of ¹⁸F-THK-5351, then at the completion of the PET scan. ¹⁸F-THK-5351 will be synthesized by the CUMC PET Department Radiochemistry Laboratory. Subjects will not be informed of ¹⁸F-THK-5351 PET scan results, as this scan is used only in research and have not yet been validated for clinical use. Subjects will be informed if a clinically important abnormality is detected on MRI or PET imaging (e.g., brain tumor).

3.1.4 Image processing

FreeSurfer (<http://surfer.nmr.mgh.harvard.edu/>), the MRI software package comprising a suite of automated tools for segmentation, reconstruction, and derivation of regional volumes and surface-based rendering, will be used for derivation of regions-of-interest (ROIs). Eleven ROIs will be extracted from the structural T1 image: entorhinal cortex, hippocampus, inferior temporal cortex, combined superior and middle temporal cortex, superior parietal lobule, inferior parietal lobule, precuneus, occipital cortex, prefrontal cortex, striatum, and thalamus.

¹⁸F-THK-5351 PET images will be analyzed as follows: Freesurfer based ROIs will be applied to coregistered PET images. Correction for partial volume effects using a region-based voxel-wise method[22] will be applied. Regional time-activity curves using 40-60 min of scan data will be extracted from the PET scans, including cerebellum which will be used as a reference region. Standardized uptake value ratio (SUVR) values will be calculated by dividing SUV values for each target region by that of the cerebellum

3.1.5. Cerebrospinal fluid sampling and analysis

Subjects will have the option of having one lumbar puncture (LP) for CSF collection. Subjects may refuse the LP and still participate in the other study procedures. CSF analysis will be performed to determine CSF concentrations of total tau, phospho-tau, β -amyloid, and markers of inflammation such as IL-1 β , TNF- α , glial fibrillary acidic protein, S100B, and YLK-40.

3.1.6. Procedures performed in other protocols

If any of the above procedures have been performed within one year of the ¹⁸F-THK-5351 PET scan, then the procedures will not need to be repeated under this protocol. Rather the previously obtained results will be used.

3.2 Primary Study Endpoints

Because the drugs used in this study are radioligands given at tracer doses, there are no clinical endpoints of the study.

The primary outcome measures are:

1. Amount of ¹⁸F-THK-5351 binding.

Secondary outcome measures are:

1. CSF concentration of inflammatory markers
2. CSF concentration of β-amyloid, tau and phospho-tau

3.3 Secondary Study Endpoints

N/A

3.4 Primary Safety Endpoints

N/A

4 Subject Selection and Withdrawal

4.1 Inclusion Criteria

1. Age 50 and older
2. Meet criteria for either a) amnestic mild cognitive impairment (single or mixed domain) or mild Alzheimer's disease, or b) have no cognitive impairment based on history, exam, neuropsychological testing, and consensus diagnosis. MCI and mild AD patients must have Clinical Dementia Rating scale score of 0.5 or 1. Unimpaired subjects must have Clinical Dementia Rating scale score of 0.
3. Subjects unable to provide informed consent must have a surrogate decision maker
4. Written and oral fluency in English or Spanish
5. Able to participate in all scheduled evaluations and to complete all required tests and procedures.
6. In the opinion of the investigator, the subject must be considered likely to comply with the study protocol and to have a high probability of completing the study.

4.2 Exclusion Criteria

1. Past or present history of certain brain disorders other than MCI or AD.

2. Certain significant medical conditions, which make study procedures of the current study unsafe. Such serious medical conditions include uncontrolled epilepsy and multiple serious injuries.
3. Contraindication to MRI scanning
4. Conditions precluding entry into the scanners (e.g. morbid obesity, claustrophobia, etc.).
5. History of kidney disease or presence of impaired kidney function based on laboratory tests at screening visit. Benign or resolved kidney conditions such as uncomplicated kidney stones or treated infection would be allowed if kidney function is normal at screening visit.
6. History of liver disease or presence of impaired liver function based on laboratory tests at screening visit. Benign or resolved liver conditions such as uncomplicated cysts or resolved viral infections would be allowed if liver function is normal at screening visit.
7. Participation in the last year in a clinical trial for a disease modifying drug for AD.
8. Inability to have a catheter in subject's vein for the injection of radioligand.
9. Inability to have blood drawn from subject's veins.

Impaired kidney function is defined here as estimated glomerular filtration rate < 60 mL/min/1.73m² at screening. Impaired liver function is defined here as aspartate aminotransferase, alanine aminotransferase, or alkaline phosphatase > 2 times upper limit of normal at screening visit.

4.3 Subject Recruitment and Screening

Up to 60 elderly men and women will be recruited from CUMC Washington Heights-Inwood Community Aging Project (known locally as WHICAP, R01 AG037212, PI [name]), the CUMC Alzheimer's Disease Research Center (ADRC), and [name] Questionable Dementia 2 (QD2) cohort, and CUMC clinics. Recruitment may come from additional research cohorts, as this protocol will encourage data sharing to reduce the total number of subjects that require ¹⁸F-THK-5351 imaging for project completion. Only subjects from established research cohorts that previously consented to be contacted about future research studies will be approached about this study. Informed consent will be obtained by a qualified investigator prior to study enrollment. Subjects will undergo screening including history, physical examination, routine laboratory studies, neuropsychological testing, and brain MRI to identify cohorts who are either cognitively impairment, meeting criteria for MCI or AD, (target n = 30), or cognitively normal (n = 30). Subjects co-enrolled from other protocols may have any of the above screening procedures done through the earlier study, as long as screening laboratories, MRI, and neuropsychological testing are done within 12 months of ¹⁸F-THK-5351 imaging.

During screening, participants will be administered a neuropsychological test battery and a medical interview. Individuals with significant cognitive or functional impairment are referred for evaluation by a board-certified physician. All participants' data will be reviewed in a consensus conference where a working diagnosis is established. The diagnostic criteria for dementia will be based on DSM-IV criteria. The diagnosis of MCI or AD will be based on updated criteria[20, 21]. The neuropsychological test battery will include the following tests: the Mini-Mental State Examination, Selective Reminding Test, Benton Visual Retention Test (BVRT), Recognition Memory Multiple Choice version, Rosen Drawing Test, 5 selected items,

BVRT Matching, multiple-choice version, Boston Naming Test, 15 selected items, The Controlled Word Association Test and Category naming: Animals, Food and Clothing, Complex Ideational Material Subtest of the Boston Diagnostic Aphasia Evaluation (BDAE): first 6 items, The Color Trails Test part 1, WAIS-R Similarities, and Color Trails part 2. At minimum, subjects will receive testing in Selective Reminding Test, Trail Making Test, and Verbal Fluency (CFL, and Animals). Raw scores and demographically corrected T-scores (age, years of education, sex, and ethnicity) will be determined. Subjects will also undergo University of Pennsylvania Smell Identification Test (UPSIT), a non-invasive test that measures odor identification abilities.

4.4 Early Withdrawal of Subjects

4.4.1 When and How to Withdraw Subjects

Subjects will be withdrawn if they develop serious medical illness during the study, defined as an event determined to be grade 3 or higher, i.e., severe or life-threatening. The exception is a single event of syncope if felt by the PI to be vasovagal in etiology and related to catheter placement or venipuncture. Vasovagal syncope in response to blood drawing and IV placement is common and does not warrant study withdrawal if the subject's loss of consciousness is brief (i.e., less than 5 minutes) and does not require further medical attention.

4.4.2 Data Collection and Follow-up for Withdrawn Subjects

Data collected prior to withdrawal will be analyzed if possible. No data collection will take place after withdrawal in subjects who drop out of the study.

5 Study Drug

5.1 Description

¹⁸F-THK-5351 is a PET radioligand that binds to tau aggregates. ¹⁸F-THK-5351 will be administered at tracer doses and is not expected to have a pharmacological effect.

5.2 Treatment Regimen

N/A

5.3 Method for Assigning Subjects to Treatment Groups

N/A

5.4 Preparation and Administration of Study Drug

¹⁸F-THK-5351 will be synthesized and administered by the CUMC PET Department. ¹⁸F-THK-5351 injection will be administered at a target imaging dose of up to 5 mCi (185 MBq).

Calculation of activity to be injected will be performed by a qualified radiopharmacist in the CUMC PET department.

5.5 Subject Compliance Monitoring

N/A

5.6 Prior and Concomitant Therapy

Subjects will not be included in the study if they have participated in the last year in a clinical trial for a disease modifying drug for AD.

5.7 Packaging

N/A

5.8 Blinding of Study Drug

N/A

5.9 Receiving, Storage, Dispensing and Return

5.9.1 Receipt of Drug Supplies

Upon receipt of the of the study treatment supplies, the CUMC PET Center staff will perform an inventory and a drug receipt log will be filled out and signed by the person accepting the shipment. Any damaged or unusable study drug in a given shipment (active drug or comparator) will be documented in the study files.

5.9.2 Storage

N/A

5.9.3 Dispensing of Study Drug

¹⁸F-THK-5351 will be administered the same day of synthesis by the CUMC PET Department.

5.9.4 Return or Destruction of Study Drug

Any unused radiopharmaceutical will be on site and documented in the study files.

6 Study Procedures

This study will involve up to 5 outpatient visits. See schedule below.

At the first screening visit, subjects will sign informed consent, undergo history and physical and neurological examination, neuropsychological testing, and have blood drawn routine safety laboratories. Additional screening visits may be required to complete all procedures. Additional visits will be required for brain MRI. Flexibility is allowed in screening procedures such that procedures may be performed in any order and may be performed on the same day if schedule allows for subject convenience. Subjects who already had screening procedures performed under a previous research protocol do not need to have them repeated unless performed more than 12

months prior to the ¹⁸F-THK-5351 PET scan. A total of 3 screening visits are anticipated. However, additional visits may be necessary if certain tests must be scheduled on different days due to scheduling.

Up to two study visits will be required. One visit will be for the ¹⁸F-THK-5351 PET scan and the second for the optional lumbar puncture. Subjects may decline the lumbar puncture and still participate in other parts of the study. If schedule allows, the ¹⁸F-THK-5351 PET and LP could be performed on the same day.

¹⁸F-THK-5351 PET scans and LP must be completed within 12 months of the brain MRI.

Study Schedule

Study Procedures	Screen ^a	Study ^b	
	≤12 months	Visit 1	Visit 2
Informed consent	X		
Medical/psychiatric history	X		
Inclusion/exclusion criteria	X	X	X
Neuropsychological testing	X		
MRI	X		
¹⁸ F-THK-5351 PET ^c		X	
Lumbar puncture ^{c, d}			X
Laboratory determinations ^e	X	X	
Neurological examination	X		
Vital signs	X		
Height and weight	X	X	
Adverse events ^f	X	X	X

a. Screening procedures may be performed in any order and may be performed on the same day if schedule allows for subject convenience. Subjects who already had screening procedures performed under a different protocol do not need to have them repeated unless performed more than 12 months prior to inclusion in this study. Up to 3 screening visits are anticipated. However, additional visits may be necessary if certain tests must be scheduled on different days due to scheduling.

b. Study procedures must be completed within 12 months of MRI.

c. ¹⁸F-THK-5351 PET and LP may be performed on same day.

d. Lumbar puncture is optional.

e. Laboratory determinations here include complete blood count, basic metabolic panel, liver functions tests, thyroid stimulating hormone, and urinalysis.

f. Adverse event reporting to be performed at Visit 1 after the PET scan is completed. Subject will be called by telephone 24 hours after the PET scan for follow up adverse event reporting.

7 Statistical Plan

7.1 Sample Size Determination

Because ¹⁸F-THK-5351 is a recently developed radioligand, we do not have adequate preliminary data for a formal power calculation. However, results from a small published study showed greater ¹⁸F-THK-5351 binding in hippocampus in AD patients (n = 3) than controls (n = 3), with effect size of 1.95[19]. This would allow us to detect differences in ¹⁸F-THK-5351 between AD patients and controls in hippocampus with n = 10 subjects per group. However, we don't know the effect size when MCI patients are compared to AD patients and when MCI

patients are compared to controls. We wish to scan up to 60 subjects total (30 impaired and 30 unimpaired) to ensure power to see effect on ¹⁸F-THK-5351 binding between groups.

7.2 Statistical Methods

The primary outcome measure will be regional standardized uptake value ratio (SUVR) values for ¹⁸F-THK-5351 using cerebellum as reference region. Multiple brain regions will be measured, with particular attention to medial temporal cortex structures such as hippocampus and entorhinal cortex. Analysis will be performed using a one-way ANOVA with cognitive status (AD vs. MCI vs. normal) as independent variable. Effect of age and education will be determined in post-hoc analysis.

Regression models will be fit for ¹⁸F-THK-5351 binding as dependent variable and cognitive scores, voxel count on MRI, and CSF concentrations of markers of inflammation and neurodegeneration as independent variables.

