Statistical Methodology	
Comparing PET imaging among groups The primary outcome measure will be regional standardized uptake value ratio (SUVR) values for ¹⁸F-THK-5351 using cerebellum as reference region. Multiple brain regions will be measured, with particular attention to medial temporal cortex structures such as hippocampus and entorhinal cortex. Analysis will be performed using a one-way ANOVA with cognitive status (AD vs. MCI vs. normal) as independent variable. Effect of age and education on ¹⁸F-THK-5351 will be determined in post-hoc analysis.
 
Sample size determination Results from a small published study showed greater ¹⁸F-THK-5351 binding in hippocampus in AD patients (n = 3) than controls (n = 3), with effect size of 1.95. This would allow us to detect differences in ¹⁸F-THK-5351 between AD patients and controls in hippocampus with n = 10 subjects per group. However, we don't know the effect size when MCI patients are compared to AD patients and when MCI patients are compared to controls. We wish to scan up to 60 subjects total (30 impaired and 30 unimpaired) to ensure power to see effect on ¹⁸F-THK-5351 binding between groups.
 
We will also perform linear regression to look for correlations between change in ¹⁸F-THK-5351 binding and cognitive scores, CSF concentration of biomarkers of inflammation and neurodegeneration, and atrophy measured with MRI.

1 Introduction

This document is a protocol for a human research study. This study is to be conducted according to US and international standards of Good Clinical Practice (FDA Title 21 part 312 and International Conference on Harmonization guidelines), applicable government regulations and Institutional research policies and procedures.

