¹⁸F-THK-5351 is a PET radioligand that binds to paired helical filament tau aggregates. This radioligand has only been used for research purposes. ¹⁸F-THK-5351 will be administered in tracer doses ($\leq 10 \mu\text{g}$) at activity of up to 5 mCi (185 MBq) per injection.

2 Study Objectives

- 2.1. The primary objective is to determine the extent and spatial distribution of tau at different stages along the cognitive spectrum of aging (cognitively normal older adults, adults with mild cognitive impairment, and adults with Alzheimer's disease dementia).
- 2.2. Secondary objectives are to determine how ¹⁸F-THK-5351 binding in brain relates to cognitive performance, amyloid binding, atrophy on MRI, and CSF concentrations of markers of inflammation and neurodegeneration.

3 Study Design

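### Section 7.2 states no head-size adjustment for its MRI predictor, and its pooled regression slopes cannot by themselves separate within-stage from between-stage association

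*Combined protocol and SAP*

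**What the plan says.** The regression plan in Section 7.2 is one sentence. It takes tracer "binding as dependent variable and cognitive scores, voxel count on MRI, and CSF concentrations of markers of inflammation and neurodegeneration as independent variables". The Study Summary (Statistical Methodology) describes the MRI predictor differently, listing "CSF concentration of biomarkers of inflammation and neurodegeneration, and atrophy measured with MRI". Objective 2.2 also names the construct as atrophy.

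On MRI, Section 3.1.3 describes a 1 mm T1 acquisition for volumetry. Section 3.1.4 says the software suite provides "derivation of regional volumes and surface-based rendering, will be used for derivation of regions-of-interest (ROIs". Neither these sections nor any other mentions intracranial volume, head size or another scaling step. Section 3.1.1 recruits men and women.

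Cognitive status enters Section 7.2 only in the primary analysis, a "one-way ANOVA with cognitive status (AD vs. MCI vs. normal) as independent variable". Section 7.3 defines one population covering all three stages. Objective 2.1 is framed "at different stages along the cognitive spectrum of aging"; objective 2.2, which the regressions serve, does not say whether its relationships are meant within or across stages.

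On numbers, Section 7.1 says "We wish to scan up to 60 subjects total (30 impaired and 30 unimpaired"), with no MCI/AD split. CSF data will be fewer, since Section 3.1.5 says "Subjects may refuse the LP and still participate in the other study procedures".

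**The concern.** There are two separate issues.

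First, a count of voxels in a region measures how much tissue is there, not how much has been lost. People with larger heads have larger regions. If the count is used unscaled, part of its variation is head size, and a real association between binding and atrophy becomes easier to miss.

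Second, binding, atrophy and CSF markers may each differ by cognitive stage. A slope fitted to all subjects together then combines differences between stages with any association among people at the same stage. Nothing in Section 7.2 says which of the two the slope is meant to describe, and no planned slope isolates the second. A reader of the results could not tell whether binding tracks atrophy among people at the same stage, or whether both simply differ between normal, MCI and AD.

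**Working it through.** **The plan's own figure.** Section 7.1 gives one sample-size figure: 10 per group for AD against controls at a hippocampal effect size of 1.95. With a two-sided 5% t-test that has 98.5% power, so 10 suffices, although the plan states neither alpha nor target power. No figure is given for the regressions, so the inputs below are assumed unless a source is named.

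**Step 1: head size.** Inputs: n = 60 (Section 7.1); true correlation r = 0.40 between binding and head-size-adjusted volume (assumed); correlation h between head size and raw regional volume (assumed); head size unrelated to binding (assumed).

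Observed correlation = r × √(1 − h²). Power ≈ Φ(atanh(observed) × √(n − 3) − 1.96).

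For h = 0.5: 0.40 × √0.75 = 0.346; atanh = 0.361; 0.361 × √57 = 2.73; Φ(2.73 − 1.96) = 78%.

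| h | observed r | power |
|---|---|---|
| adjusted | 0.400 | 89% |
| 0.2 | 0.392 | 88% |
| 0.4 | 0.367 | 83% |
| 0.5 | 0.346 | 78% |
| 0.6 | 0.320 | 71% |

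**Step 2: what the pooled slope contains.** Give both variables unit SD within stage and within-stage correlation ρ. With 30 + 30 subjects and a gap of d SD on both variables, the expected pooled slope is (ρ + d²/4) / (1 + d²/4). With ρ = 0 this is 0.0625/1.0625 = 0.06 at d = 0.5 and 0.25/1.25 = 0.20 at d = 1.0. The slope is non-zero from stage differences alone.

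Simulation: 20,000 samples, ρ = 0, one predictor per model, two-sided 5% t-test of the slope, split 30 normal / 15 MCI / 15 AD (split and gaps assumed). Share of samples with a significant slope:

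| stage means, normal/MCI/AD (SD) | pooled | two-level term | three-level term |
|---|---|---|---|
| 0/0.5/0.5 on both | 7% | 5% | 5% |
| 0/0.8/0.8 on both | 18% | 5% | 5% |
| 0/1.0/1.0 on both | 34% | 5% | 5% |
| 0/0.5/1.0 on both | 20% | 5% | 5% |
| 0/0.5/1.5 on both | 59% | 14% | 5% |
| binding 0/0.5/1.95, predictor 0/0.5/2.0 | 92% | 39% | 5% |

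With the plan's 1.95 as the AD-control binding gap, MCI midway and an assumed predictor gap of 1.0 SD, the pooled figure is 47%. Section 7.2 does not say whether predictors enter jointly. If a cognitive score with an assumed 2 SD gap is in the same model, the first three pooled figures become 6%, 9% and 13%. An impaired/unimpaired term is not enough once MCI and AD differ substantially; the three-level term is.

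**Step 3: what adjustment costs.** Assume within-stage ρ = 0.30 and n = 60. The adjusted slope targets 0.30. With MCI equal to AD, the pooled slope targets (0.30 + 0.0625)/1.0625 = 0.34 at gaps of 0.5 SD and (0.30 + 0.25)/1.25 = 0.44 at 1.0 SD.

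Approximate standard error = √((1 − slope²)/residual df), with 58 df pooled and 56 adjusted:
- pooled, 0.5 SD gaps: √(0.8836/58) = 0.1234
- pooled, 1.0 SD gaps: √(0.8064/58) = 0.1179
- adjusted: √(0.91/56) = 0.1275

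The adjusted standard error is therefore 1.03 to 1.08 times the pooled one. Simulated power is 64% adjusted, against 78% and 95% pooled. For CSF subsets of 40 (20/10/10) and 30 (15/8/7), with uptake assumed, adjusted power is about 46% and 35%.

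**The case against.** Four points can be made for the plan.

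First, the absence of head-size scaling is inferred from silence. Section 3.1.3 uses voxel count for the image matrix, so the term is used loosely, and in Section 7.2 it may be shorthand for the regional volumes of Section 3.1.4. A reader might infer that the atrophy analysis is known to be uncorrected; the documents do not support that. What stands is that the analysis plan names a count and gives no scaling step anywhere.

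Second, a reader might infer that the pooled slope is wrong, or that the 7% to 92% are false positives. Neither follows. Objective 2.2 does not ask a within-stage question, Section 7.3 pools the stages, and those significant results correctly detect an association across the spectrum. They mislead only if read as within-stage tracking. This objection stands in full, and the pooled slope should stay.

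Third, adjustment is less suitable for cognition. The consensus diagnosis in Section 4.3 draws on the neuropsychological battery, and under Section 4.1 "MCI and mild AD patients must have Clinical Dementia Rating scale score of 0.5 or 1". Adjusting for status therefore removes part of the predictor itself. This also stands, and limits the fix.

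Fourth, almost every magnitude is assumed. The only effect size in the documents, 1.95, comes from three patients and three controls. The ranges are illustrative, and at their low ends (one point of power; 7% against 5%) they hardly matter.

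**Conclusion.** The point holds as an inexpensive improvement to secondary analyses. Section 7.2 does not say how its MRI predictor becomes a measure of atrophy, and it offers no slope that separates association within a stage from association across stages.

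The head-size loss is negligible if head size correlates 0.2 with regional volume (89% to 88%) and material from about 0.4 (83% or lower), provided head size is unrelated to binding. The gap between pooled and within-stage readings ranges from trivial to very large with the assumed stage gaps; only the three-level term holds the rate at 5% throughout.

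A reader might take 64% power against 78% to 95% as a loss of precision from adjustment. It is mostly a different target: the standard error rises only about 3% to 8%, while the association being estimated falls from 0.34 or 0.44 to 0.30.

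The primary ANOVA is unaffected. Joint or single entry of predictors, CSF counts and confidence intervals are missing detail rather than part of this defect.

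**What to change.** Amend Section 7.2 in two places.

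(a) Replace the voxel-count predictor with regional MRI volume adjusted for intracranial volume, as a ratio, a residual or a covariate, and say which. This assumes that intracranial volume can be derived from the T1 scan already acquired.

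(b) For the atrophy and CSF regressions, report beside each pooled slope one adjusted for the three-level status already used in the ANOVA, not an impaired/unimpaired term. Label the pooled slope as association across the cognitive spectrum, and claim within-stage association only from the adjusted slope. For cognition, keep the pooled slope as the main result and treat the adjusted slope as a sensitivity analysis.

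The cost is a few lines of text and a few model terms, with no new data collection. The downside is limited power for the within-stage question, especially in the CSF subset, so a non-significant adjusted slope should not be read as evidence of no association.
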